### **Specific Aim 3: Explore the relationship between prefrontal activity and behavioral outcomes**

fnIRS of prefrontal cortex will be used to quantify changes in prefrontal/executive activity during performance of the *Figure-8 Walk Test* and *EXAMINER* test to probe mechanisms of response to the interventions.

---

## **6. Research Plan:**

### Study Overview

All study procedures will be conducted at the University of Florida.

Up to thirty older men and women will be enrolled in the intervention component of this study. A larger number will be enrolled for onsite screening, because some will fail the screening tests and not proceed to the study intervention. Volunteers will undergo the following sequence of events:

- *Telephone Screening*: Volunteers will be screened by telephone to determine if they meet basic enrollment criteria including age and general health status.
- *1st Informed Consent and Onsite Screening*: Volunteers who pass the phone screen will be invited to participate in on-site screening. Informed consent for screening will be obtained. Mobility function and cognitive screening will be conducted, including 10m walk speed and tests from the cognitive battery of the NIH Toolbox. Other criteria listed in Table 6 will also be evaluated. Screening will be conducted over two visits lasting approximately 4 hours and 3 hours, respectively. A third visit may sometimes be needed if all assessments cannot be completed in the two visits
- *2nd Informed Consent and Baseline Assessment*: Qualifying volunteers will be invited to participate in the full study. They will attend a baseline assessment session which will include Informed Consent for full study participation and tests of the primary and secondary study outcomes including Figure-8 walk test and NIH EXAMINER battery of executive function. Secondary outcomes will also be evaluated as described in the Research Plan. This visit will last approximately 3 hours.
- *Rehabilitation Intervention*: Enrolled participants will receive 18 sessions of neurorehabilitation, which will be combined with either active or sham tDCS. These sessions will be completed over the course of 6 weeks. Each session will last about 75 minutes from arrival to departure.
- *Post-Intervention Assessment*: At the completion of the neurorehabilitation program, participants will attend a post-therapy assessment session that is identical to the baseline assessment.
- *Three month follow up Assessment*: Three months after completing the neurorehabilitation program, participants will attend a 3-month follow up assessment session that is identical to the baseline and post-treatment assessments.

---

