#### ***Exclusion criteria***

- Contraindications to non-invasive brain stimulation and/or MRI including metal in the head, pacemaker, known abnormal cranial fissures/holes.
- difficulty communicating with study personnel
- uncontrolled hypertension at rest (systolic > 180 mmHg and/or diastolic > 100 mmHg)
- Low vision that cannot be corrected by wearing glasses. Low visual will be operationally defined as visual acuity less than 20/70 on a standard eye chart, or difficulty performing complex walking tasks due to visual conditions affecting accurate navigation around and over obstacles (self-reported or observed by examiner).
- use of medications that are known to modify tDCS effectiveness including those with anticholinergic, GABAergic, or glutamatergic properties; or sodium channel blockers.
- illiterate, due to the likelihood of difficulties performing some of the cognitive tasks
- non-English speaking, due to the likelihood of difficulties following instructions during therapy and during assessments
- clinical judgment of investigative team

At the discretion of the Principal Investigator, any individual may be deemed ineligible for further participation in any component of this study if there are concerns about the individual's capability to perform study procedures or if it may be unsafe for the volunteer to participate in the study. Furthermore, minor exceptions to the inclusion/exclusion criteria may be permitted at the discretion of the Principal Investigator if those exceptions do not influence participant safety. For example, small deviations from the target range of walking speed or cognitive performance. This is important to ensure that individuals are not excluded for insignificant reasons and to facilitate meeting enrollment benchmarks.

---

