### Assessment sessions

Assessments will be conducted at the following time points:

*Baseline* - generally within two weeks before starting the intervention

*Post-Intervention* – generally within one week after completing the intervention

*3-month follow-up* - generally about three months after completing the intervention

The following assessments will be completed at each intervention:

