### **Rehabilitation Intervention**

Participants will take part in a 6-week, 18-session neurorehabilitation led by qualified and trained study personnel. Participants will be randomized to one of three groups: 1) standard walking neurorehabilitation with sham tDCS ('standard/sham' group), 2) complex walking neurorehabilitation with sham tDCS ('complex/sham' group), or 3) complex walking neurorehabilitation with active anodal tDCS ('complex/active' group). Training logs will be maintained to gauge the content and intensity of training. To control for intensity, participants will maintain a rating of perceived exertion of 4 (moderate to strong) on the Borg Category/Ratio Scale during walking. Exertion will be adjusted by modifying walking speed and/or by modifying the rest time between walking bouts. Training logs will also include information on attendance and adverse events. From these logs we will determine adherence (# of sessions attended), retention (completion of rehabilitation and post-therapy assessment) and number of adverse events.

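### Both outcome visits are timed from completing training and none is scheduled for early stoppers, so the effect sizes that will power the full trial would rest on completers

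*Combined protocol and SAP*

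**What the plan says.** Each timing statement for a post-baseline assessment is tied to finishing training.

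- **Study Overview, post-intervention visit:** "At the completion of the neurorehabilitation program, participants will attend a post-therapy assessment session that is identical to the baseline assessment".
- **Study Overview, follow-up visit:** "Three months after completing the neurorehabilitation program, participants will attend a 3-month follow up assessment session".
- **Assessment sessions:** the windows are "generally within one week after completing the intervention" and "generally about three months after completing the intervention".
- **Post-Intervention Assessment and 3-Month Follow-Up Assessment:** this adds only that procedures match baseline.

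The program is 18 sessions over six weeks. The Study Overview states as an expectation that "Enrolled participants will receive 18 sessions of neurorehabilitation, which will be combined with either active or sham tDCS", and does not say what follows if someone receives fewer.

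Under Rehabilitation Intervention, the training logs yield "adherence (# of sessions attended), retention (completion of rehabilitation and post-therapy assessment) and number of adverse events". Retention therefore needs both the training and the assessment to be complete.

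The Statistical Analysis Plan (section 10) computes effect sizes from group mean differences and standard deviations for each hypothesis's primary outcome, and uses them to plan the full trial's power. It names no analysis set and no method for missing outcomes.

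In the screening section, under Exclusion criteria, the Principal Investigator is given discretion under which "any individual may be deemed ineligible for further participation in any component of this study". The grounds are doubts about capability to perform study procedures, or safety.

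**The concern.** A participant who stops partway through training never reaches the event from which both visits are dated, so a team following the text has no date on which to book either one. The retention definition points the same way, because it has no category for someone who stopped training but was still assessed. With the analysis plan silent on who is analysed, the effect sizes fall to completers by default.

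This matters because estimating effect size and variance for a later trial is the study's stated purpose, and Hypotheses 1a and 1b rank the three arms on effect size. Stopping could plausibly be related to outcome. Participants are over 65 and selected for slow walking and lower executive scores. Two arms train on obstacles, soft surfaces, dim lighting, ramps and stairs, and one on steady walking only. If poorer performers left a harder arm unmeasured, that arm would look better than the randomised comparison supports, and their later outcomes could not be recovered.

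**Working it through.** **Step 1: reading the schedule.** The four timing statements (two in Study Overview, two in Assessment sessions) use completion of the program or intervention as the anchor. None uses randomisation, first session or planned end date. No section describes an early-termination visit or continued assessment after training stops. The gap is confirmed for people who stop early. It is less clear for people who merely miss sessions: completion is not defined and adherence is a count of sessions attended, so someone who reaches the end of the program with absences may still be assessed.

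**Step 2: size of the effect.** The plan states no effect size, standard deviation, dropout rate, alpha, power or allocation ratio, so there is no figure to reproduce. The only document inputs are up to 30 participants and three groups. Everything else here is assumed: equal allocation (30 / 3 = 10 per arm), the stopping rates, the gain in stoppers, and 80% power at two-sided 5% for the future two-arm comparison.

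Let f1 and f2 be the shares stopping early in the two arms, and k the number of SDs by which stoppers do worse than completers. Then:

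- bias of the completer contrast = (f1 − f2) × k
- overstatement of one arm's own change = f × k

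*One-sided stopping.* Completers gain 0.50 SD over control, stoppers gain nothing (k = 0.5), and nobody stops in control.

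- 2 of 10 stop: 0.8 × 0.50 + 0.2 × 0 = 0.40, a bias of 0.10.
- 1 of 10 stops: 0.9 × 0.50 = 0.45, a bias of 0.05.
- Mixing stoppers and completers also widens the SD slightly. With 2 of 10, that arm's variance is 1 + 0.8 × 0.2 × 0.5² = 1.04. Pooled with 1.00 this is 1.02, SD 1.010, and 0.40 / 1.010 = 0.396. The simpler 0.40 is adequate.

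*Stopping in both arms.*

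- f1 = f2 with equal k: the contrast bias is 0. Each arm's own change is still overstated by f × k, which is 0.05 to 0.20 SD for 10–20% stopping and k of 0.5 to 1.0.
- Stopping rates 10 to 20 points apart, k of 0.5 to 1.0: the bias is 0.05 to 0.20 SD.

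*Consequence for the full trial* (two-sample t-test):

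| Effect over all randomised | n per arm for 80% power | Power if 64 per arm were used |
|---|---|---|
| 0.50 | 64 | 80% |
| 0.45 | 79 | 71% |
| 0.40 | 100 | 61% |

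**Step 3: comparison with the pilot's own imprecision.** The 95% half-width for d is 1.96 × √(2/n + d²/(4n)). At d = 0.5 and n = 10 this is 1.96 × √(0.2 + 0.00625) = 1.96 × 0.454 = 0.89. With 8 assessed per arm it is 1.00. The 0.10 shift is about one-ninth of the half-width (0.10 / 0.89 = 0.11).

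**The case against.** **The plan does not exclude early stoppers.** A reader might infer that they are barred from assessment and that a completer analysis is prescribed. Neither is stated. The exact position is that no visit is scheduled for them; the completer basis follows from the schedule together with a silent analysis plan. This corrects the wording but does not close the gap.

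**Differential stopping would be visible.** Attendance, retention and adverse events are logged, Hypothesis 2 compares them between interventions, and baseline outcomes exist for everyone who attends that visit. It would therefore be wrong to say the study could not detect unequal stopping, or could not tell whether stoppers were worse at baseline. Only their later outcomes would be missing. That objection stands.

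**The arms are partly matched.** All groups train to the same perceived exertion, so intensity is controlled although task complexity is not. The two complex arms do the same walking training, so task difficulty cannot explain different stopping between them. A reader might infer that the complex arms will be flattered; the documents do not establish that, or any direction of bias.

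**The investigator's discretion is probably about eligibility.** A reader might take it as a second route out after randomisation. It sits among the screening criteria and speaks of ineligibility, so eligibility is the natural reading. The words are broad enough to need clarifying, no more.

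**A fixed week-6 visit for everyone has a cost.** It would remove the drift in visit date for slow finishers, but would test them before training ends and so no longer measure post-treatment response. For that reason the present timing should stay for those who finish.

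**It is a pilot.** Its imprecision exceeds any bias illustrated here. That limits the importance of the point. It does not justify an avoidable selection of who is measured.

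**Conclusion.** The concern holds in a limited form. Both post-baseline assessments depend on completing training, retention merges training with assessment, and no outcome visit is scheduled for a randomised participant who stops early. Followed as written, the effect sizes carried into the full trial would describe completers.

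Whether that biases the contrasts depends on stopping differing by arm, or in its severity, and being related to outcome; the documents support neither assumption nor its opposite. On the assumed one-sided case, 0.50 becomes 0.40, and a full trial sized at 64 per arm would have 61% power instead of 80%. With equal stopping of equal severity the contrast is unaffected, though each arm's change is overstated and precision falls. The shift is small against a half-width of about 0.89. The point merits a change because the remedy is specific and cheap and the lost outcomes cannot be collected later, not because a large bias has been shown.

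**What to change.** 1. **Study Overview and Assessment sessions:** keep the current timing for participants who finish. For those who stop early, schedule the same two assessments at the planned end of the six-week program and three months after that. Invite every randomised participant, where safe, unless consent for follow-up is withdrawn.
2. **Rehabilitation Intervention:** report completion of training separately from completion of the outcome assessment, by arm.
3. **Statistical Analysis Plan:** base the primary effect sizes on all participants as randomised who have an outcome, with completers as a secondary summary.
4. **Exclusion criteria:** ask the sponsor to state whether the discretion clause applies after randomisation, and to reconcile it with the assessment schedule. No rule on removal or stopping is proposed here.

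The cost is a wording amendment and the recall of a few early stoppers for visits of a kind already planned. Effect sizes may come out slightly smaller. Some early stoppers will decline, so the change reduces the selection but may not remove it.

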### Telephone Screening

Participants will be screened by telephone to determine if they meet the following inclusion criteria:

- over the age of 65
- able to walk independently without a walker (canes are OK)

- find it physically tiring to walk a quarter mile, or climb two flights of stairs, or perform household chores. (At least one of these should be true).
- do not feel severe pain in legs when walking (i.e., pain that prevents performing daily walking tasks).
- In the past six months, have not fractured or broken a bone.
- have not been diagnosed with an overt injury or illness to the central nervous system (Parkinson's disease, Alzheimer's disease, stroke, brain injury, spinal cord injury, etc.).
- do not have a terminal illness.
- do not have uncontrolled high blood pressure.
- do not have severe arthritis, such as awaiting joint replacement
- do not have current cardiovascular, lung or renal disease; diabetes; terminal illness
- have not had myocardial infarction or major heart surgery in the previous year
- have not had cancer treatment in the past year, except for nonmelanoma skin cancers and cancers having an excellent prognosis (e.g., early stage breast or prostate cancer)
- do not have a current diagnosis of schizophrenia, other psychotic disorders, or bipolar disorder
- not currently participating in physical therapy for lower extremity function or cardiopulmonary rehabilitation
- not currently enrolled in any clinical trial
- not recently enrolled in a clinical trial that may affect physical or cognitive abilities
- not planning to relocate out of the area during the study period
- no known contraindications to non-invasive brain stimulation and/or MRI including metal in the head, pacemaker, known abnormal cranial fissures/holes.

---

### ***1st Informed Consent and Onsite Screening***

Upon arriving to the research site, participants will undergo informed consent for screening and functional assessments. All questions from the phone screening will be repeated, and additional health/medical screening criteria will be evaluated as noted in the table below. As part of screening, we will explain in the detail the full study protocol including rehabilitation intervention with transcranial direct current stimulation.

Screening will usually occur over two separate study visits, occurring within a span of about 1-2 weeks. The following assessments will be conducted during the screening visit:

- 10-meter walking speed
- NIH Toolbox: A subset of the NIH Toolbox cognitive battery will be conducted, with emphasis on tests of attention, executive functions, and working memory. This testing can be completed in 30 minutes.
- Activities Specific Balance Confidence Scale: The ABC Scale is a 16-item questionnaire that gauges confidence (on a scale of 0-100%) on various balance and walking tasks relevant to household and community ambulation.
- Tests of foot tactile sensation. This includes touching a vibrating probe to the foot, as well as pressing plastic probes or monofilaments (similar to hairbrush bristles) of various size/stiffness to the sole of the foot to determine sensitivity of sensation.
- Resting blood pressure
- Basic visual examination with standard eye chart
- Height, weight, age, sex
- Obtain list of medications that the participant is currently using

- Walking test with active or sham transcranial direct current stimulation (tDCS). For full details about tDCS, please see section below (Rehabilitation Intervention; Transcranial direct current stimulation). This test serves two purposes. One is to allow the participants to experience tDCS prior to enrolling in the study intervention. This will help to fully inform the participants and may help us to avoid drop-outs. The second purpose is to allow us to collect cross sectional data to assess whether active tDCS aids with motor learning in the context of walking. This is consistent with the overall aims of the study. The walking test will involve a walking course of 40 foot length where there will be small foam obstacles to step over and soft mats to walk across. We will ask the participants to walk at their fastest safe speed. They will be asked to do this task 10-15 times in a row, with approximately 1-2 minutes of rest in between every walking trial. Performance on each walking trial will be measured as walking speed. During this test, participants may be asked to wear an accelerometer (activity monitor) so we can assess how smoothly they walk. They may also be asked to wear sensors on their fingers that measure skin conductivity, which is a probe of sympathetic nervous system arousal.
- Videos and/or photos may be taken during assessments to document the functional abilities of participants, and for possible use in research presentations or education. At the time of consent, participants will choose what their videos/photos can be used for. We will avoid capturing images of the participants face, and will delete any such images that are accidentally captured.

Following the screening visit, study staff will evaluate performance/responses relative to the following study enrollment criteria. Individuals who meet all criteria will be invited to enroll in the full study (i.e., the rehabilitation intervention).

### **Screening Criteria**

#### ***Inclusion criteria***

- preferred 10m walking speed < 1.0 m/s
- less than 50th percentile rank (age and education corrected score) on NIH toolbox executive assessments: Card Sort Test and Flanker test
- Willingness to be randomized to either intervention and to participate in all aspects of study assessment and intervention

#### ***Exclusion criteria***

- Contraindications to non-invasive brain stimulation and/or MRI including metal in the head, pacemaker, known abnormal cranial fissures/holes.
- difficulty communicating with study personnel
- uncontrolled hypertension at rest (systolic > 180 mmHg and/or diastolic > 100 mmHg)
- Low vision that cannot be corrected by wearing glasses. Low visual will be operationally defined as visual acuity less than 20/70 on a standard eye chart, or difficulty performing complex walking tasks due to visual conditions affecting accurate navigation around and over obstacles (self-reported or observed by examiner).
- use of medications that are known to modify tDCS effectiveness including those with anticholinergic, GABAergic, or glutamatergic properties; or sodium channel blockers.
- illiterate, due to the likelihood of difficulties performing some of the cognitive tasks
- non-English speaking, due to the likelihood of difficulties following instructions during therapy and during assessments
- clinical judgment of investigative team

At the discretion of the Principal Investigator, any individual may be deemed ineligible for further participation in any component of this study if there are concerns about the individual's capability to perform study procedures or if it may be unsafe for the volunteer to participate in the study. Furthermore, minor exceptions to the inclusion/exclusion criteria may be permitted at the discretion of the Principal Investigator if those exceptions do not influence participant safety. For example, small deviations from the target range of walking speed or cognitive performance. This is important to ensure that individuals are not excluded for insignificant reasons and to facilitate meeting enrollment benchmarks.

---

## **2nd Informed Consent and Baseline Assessment**

Participants will complete a 2nd informed consent in order to take part in the full study procedures. All study procedures will be described in detail and all questions will be answered.

### Assessment sessions

Assessments will be conducted at the following time points:

*Baseline* - generally within two weeks before starting the intervention

*Post-Intervention* – generally within one week after completing the intervention

*3-month follow-up* - generally about three months after completing the intervention

The following assessments will be completed at each intervention:

### Walking and Balance Tests

*Figure-8 Walk Test*: this test involves walking in straight and curved paths and was designed to represent walking skill in everyday life [92]. It has been shown to be associated with executive functions and performance on various other mobility-related tests in older adults [92].

*Other “complex” walking tasks*: Participants will be asked to perform a battery of walking tasks that are designed to be similar to conditions that are encountered in the home and community settings. These tasks may include walking over/around obstacles, walking while carrying an object, walking in dim lighting, walking while performing a cognitive task, walking up/down stairs, walking over a soft foam surface (exercise mats), walking backwards, gait initiation, gait termination, and/or similar tasks, and/or or a combination of these tasks.

*Quiet standing on a force platform*: This test measures center of pressure and sway during quiet standing with eyes open and with eyes closed.

*Berg Balance Scale*: A 14-item scale designed to measure balance of the older adult in a clinical setting.

During these tests, prefrontal cortical activity will be recorded with functional near infrared spectroscopy, which is described below. Participants may also be asked to perform these tasks while wearing textured shoe insoles that mildly increase sensation from the soles of the feet.

